### **8.2.6. Summary of Patient Death**

AEs where the outcome recorded as 'fatal' and/or seriousness is recorded as 'death' will be tabulated by system organ class and preferred term. Counts will be given for both system organ class and preferred term. Deaths will be identified within the relevant preferred term.

### **8.3. PREDOMINANT INTEGRATION SITE TEST**

Predominant integration site is defined as an integration site which has a density of at least 50% of the total signal detected by PCR, when the percentage of cells marked by the vector (quantitative OZ1/LNL6 DNA PCR) is greater than 1% of the test cell population. Results are recorded as part of the initial study information and at each follow-up visit.

A confirmed finding of a predominant integration site is a finding that is present on at least 2 consecutive samples. A predominant integration site finding will be reported as an SAE. Predominant integration site results will be listed only, no summary tables will be presented.

### **8.4. CBC/DIFFERENTIAL AND PLATELETS**

CBC/differential and platelets (haematocrit, red blood count, haemoglobin, white blood count, platelets, neutrophils, lymphocytes, monocytes, eosinophils, basophils) will be recorded as part of the initial study information and at each follow-up visit. CBC/differential and platelets data will be recorded in the units as pre-printed on the CRF. No conversion of these data to Standard International Units will be required.

CBC/differential and platelets values and change from baseline (2 years post infusion or nearest timepoint before starting long term follow-up) values will be summarized overall.

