9.2 Safety Evaluations

All AE data will be coded to a System Organ Class and Preferred Term using the current MedDRA coding dictionary.

Clinical history, physical examination findings, CBC and AEs will be listed and summarized in a tabular form. AE data will be summarized annually for regulatory reporting.

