Appendix 1:
ATCG Toxicity Grading Table

SERIOUS OR LIFE-THREATENING AE's

ANY clinical event deemed by the clinician to be serious or life-threatening should be considered a grade 4 adverse experience. Clinical events considered to be serious or life-threatening include, but are not limited to:

seizures, coma, tetany, diabetic ketoacidosis, disseminated intravascular coagulation, diffuse petechiae, paralysis, acute psychosis

PARAMETER	GRADE MILD	GRADE MODERATE	GRADE SEVERE	GRADE POTENTIALLY LIFE-THREATENING
HEMATOLOGY				
Hemoglobin	8.0g/dL - 9.4g/dL	7.0g/dL - 7.9g/dL	6.5g/dL - 6.9g/dL	< 6.5g/dL
Absolute Neutrophil Count	1000 -1500/mm ³	750 -999/mm ³	500 -749/mm ³	< 500/mm ³
Platelets	75,000 - 99,000/mm ³	50,000 - 74,999/mm ³	20,000 - 49,999/mm ³	< 20,000/mm ³
Prothrombin Time (PT)	> 1.0 - 1.25 X ULN	> 1.25 - 1.5 X ULN	> 1.5 - 3.0 X ULN	> 3.0 X ULN
BT	> 1.0 - 1.66 X ULN	> 1.66 - 2.33 X ULN	> 2.33 - 3.0 X ULN	> 3.0 X ULN
Methemoglobin	5.0 - 10.0%	10.0 - 15.0%	15.0 - 20.0%	> 20.0%
CHEMISTRIES				
SODIUM				
Hyponatremia	130 - 135meq/L	123 - 129meq/L	116 - 122meq/L	< 116meq/L
Hypernatremia	146 - 150meq/L	151 - 157meq/L	158 - 165meq/L	> 165meq/L
POTASSIUM				
Hyperkalemia	5.6 - 6.0meq/L	6.1 -6.5meq/L	6.6 - 7.0meq/L	> 7.0meq/L
Hypokalemia	3.0 - 3.4meq/L	2.5 - 2.9meq/L	2.0 - 2.4meq/L	< 2.0meq/L
PHOSPHATE				
Hypophosphatemia	2.0 - 2.4 mg/dL	1.5 - 1.9 mg/dL	1.0 - 1.4 mg/dL	< 1.0 mg/dL
CALCIUM				
Hypocalcemia	7.8 - 8.4 mg/dL	7.0 - 7.7 mg/dL	6.1 - 6.9 mg/dL	< 6.1 mg/dL
Hypercalcemia	10.6 - 11.5 mg/dL	11.6 - 12.5 mg/dL	12.6 - 13.5 mg/dL	> 13.5 mg/dL
MAGNESIUM				
Hypomagnesemia	1.2 - 1.4 meq/L	0.9 - 1.1 meq/L	0.6 - 0.8 meq/L	< 0.6 meq/L
BILIRUBIN	> 1.0 - 1.5 x ULN	> 1.5 - 2.5 x ULN	> 2.5 - 5.0 x ULN	> 5.0 x ULN
GLUCOSE				
Hypoglycemia	55 - 64 mg/dL	40 - 54 mg/dL	30 - 39 mg/dL	< 30 mg/dL
Hyperglycemia (nonfasting and no prior diabetes)	116 - 160 mg/dL	161 - 250 mg/dL	251 - 500 mg/dL	> 500 mg dL
Triglycerides	-----	400 - 750 mg/dL	751 - 1200 mg/dL	> 1200 mg/dL
Creatinine	> 1.0 - 1.5 x ULN	> 1.5 -3.0 x ULN	> 3.0 -6.0 x ULN	> 6.0 x ULN
URIC ACID				
Hyperuricemia	7.5 - 10.0 mg/dL	10.1 - 12.0 mg/dL	12.1 - 15.0mg/dL	>15.0mg/dL

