## 5. OVERALL CONSIDERATIONS

All summary tables and data listings produced by INC will use the statistical package SAS (v9.2 or a more recent version).

In general, categorical data will be presented using counts and percentages, whilst continuous data will be presented using the descriptive statistics, mean, standard deviation (SD), median, minimum, maximum and number of patients with an observation (n). Minimum and maximum values will be quoted to the number of decimal places as recorded on the CRF; means, medians and SDs will be quoted to one further decimal place. Percentages will be rounded to one decimal place. Percentages smaller than 0.1 will be presented as <0.1. Percentages whose numerator is zero will be reported as zero.

All data recorded on the Case Report Form (CRF) and any derived data will be listed for all patients.

The Safety population will be used to present Adverse Event and death data. The PP population will be used to present all data .

Unless otherwise stated missing data will not be imputed. Patients who withdraw prematurely will have their data summarized at the last attended visit. Repeat assessments will not be summarized unless otherwise indicated but will be fully listed. Similarly, data collected at unscheduled visits will be listed only. Repeat and unscheduled visits will be identified on the data listings.

Where of interest, presentation of data will be pooled to reflect the target cell type, CD4 cells in OZ1-HV1-101 and CD34 cells in OZ1-HV1-102 and OZ1-HV1-202 in addition to presenting separately and overall.

<Protocol: Janssen OZ1-HV1-101/102/202>

<INC code: 1003733>

<SAP Version: 3.0>

---

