## 15. INDEX OF LISTINGS

Listing Number	Listing Description
16.2.1.1	Discontinuation Details By Study and Patient All Patients
16.2.1.2	Patient Re-instatement Details By Study and Patient All Patients
16.2.1.3	Reason for Exclusion from Analysis Populations By Study and Patient All Patients
16.2.2	Demographic Details By Study and Patient All Patients
16.2.3	Significant Medical History By Study and Patient All Patients
16.2.4	Initial Study Information Treatment Details By Study and Patient All Patients
16.2.5.1	Compliance Visit Attendance By Study and Patient All Patients
16.2.5.2.1	PBMC Analysis Details OZ1 & LNL6 DNA PCR By Study and Patient All Patients
16.2.5.2.2	PBMC Analysis Details OZ1 & LNL6 DNA PCR By Study and Patient Patients with Quantifiable Measurements
16.2.5.2.3	PBMC Analysis Details OZ1 RNA RT-PCR Study OZ1-HVI-202 All Patients
16.2.5.2.4	PBMC Analysis Details RCR By Study and Patient All Patients
16.2.6	Predominant Integration Site Marking >1% By Study and Patient All Patients
16.2.7	Integration Re-Test Details By Study and Patient All Patients
16.2.8.1	Patient Death By Study and Patient

<Protocol: Janssen OZ1-HV1-101/102/202>

<INC code: 1003733>

<SAP Version: 3.0>

	All Patients
16.2.8.2	Serious Adverse Events By Study and Patient All Patients
16.2.8.3	Non-Serious Related Adverse Events By Study and Patient All Patients
16.2.9	Central Laboratory Testing Blood Collection Details By Study and Patient All Patients
16.2.10	RCR Test Details By Study and Patient All Patients
16.2.11	CBC/Differential and Platelets By Study and Patient All Patients
16.2.12	Clinical History By Study and Patient All Patients (Pgm Note: Incorporate flag to determine whether data was collected at clinical visit or telephone contact)
16.2.13	Physical Examination By Study and Patient All Patients

<Protocol: Janssen OZ1-HV1-101/102/202>

<INC code: 1003733>

<SAP Version: 3.0>

Janssen - OZ1-HVI-101/102/202

TABLE 14.1.1

Page x of y

Patient Disposition  
Including Reason for Discontinuation  
Summary Statistics: All Patients

	OZ1-HV1-101 (N = X) n (%)	OZ1-HV1-102 (N = XX) n (%)	OZ1-HV1-202 (N = XX) n (%)	Overall (N = XX) n (%)
Patients Ongoing (Never Discontinued)				
Patients Discontinued (and Re-instated)				
Reason				
Patient request				
Randomized to placebo arm in OTH/OZ1-INT-1				
Lost to follow up				
Regulatory authority request				
Study termination				
Other				
Patients Discontinued (Never Re-instated)				
Reason				
Patient request				

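### CBC is summarized by visit and listed by patient, but no table counts product recipients who moved to, or stayed in, a worse toxicity grade, although the protocol already holds the limits

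*SAP*

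**What the plan says.** - **Summary.** SAP 8.4 covers "CBC/differential and platelets values and change from baseline" and says that these "values will be summarized overall", which means one pooled block. Baseline is the two-year value, or the nearest one before follow-up began.
- **Statistics.** SAP 5 says "continuous data will be presented using the descriptive statistics, mean, standard deviation (SD), median, minimum, maximum", with n. The Table 14.5.X shell prints this set at each visit, for both the result and the change, in the PP population (patients who received OZ1, LNL6 or both).
- **Listing.** SAP 5 says "All data recorded on the Case Report Form (CRF) and any derived data will be listed for all patients", and SAP 15 includes Listing 16.2.11, "CBC/Differential and Platelets By Study and Patient All Patients".
- **Unscheduled and repeat values.** Under SAP 5, unscheduled values are only listed, and repeats are not summarized unless stated otherwise.
- **Protocol requirement.** Protocol 9.2 says "Clinical history, physical examination findings, CBC and AEs will be listed and summarized in a tabular form".
- **Grade limits.** The Protocol Appendix 1 hematology block has limits for hemoglobin, "Absolute Neutrophil Count" and platelets. No current analysis text applies them to CBC.

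**The concern.** The safety objectives are clonal expansion and insertional oncogenesis, which are rare events in individual patients. A visit-by-visit summary of a pooled group describes the group. It does not say how many patients developed a low count, whether the count was already low at baseline, or whether the same patient was low at the next visit.

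The adverse event tables do not fully cover this. Under Protocol 10.2 a non-serious event reaches the CRF only if it is judged at least possibly related. In HIV patients a low count can readily be attributed to the disease or its treatment.

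At stake is what the final report can say. From the planned tables it cannot state how many product recipients had a new or persistent graded cytopenia.

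**Working it through.** The documents give no sample size, power or alpha for CBC, so there is no planned figure to reproduce. The check has three steps.

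**1. Which tests are unconditional.** The Protocol Time and Events Schedule has CBC and quantitative marking PCR at every visit. Integration-site work follows only when marking is at least 1%. Under Protocol 7.2, RCR testing needs a relevant adverse event or an earlier positive result. CBC is therefore the only unconditional hematology test, but not the only unconditional laboratory test.

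**2. Where one patient's falling count would appear.**

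| Output | What it shows | What it lacks |
|---|---|---|
| Table 14.5.X | Minimum and maximum of value and change, by visit | Patient, count, link between visits, split by study, unscheduled values |
| Listing 16.2.11 | Each patient's values | Grade or trend flag; not named among the Data Review Meeting listings in SAP 4, though others may be added |
| Table 14.4.1 | Patients with a new or worse hematologic disorder, by visit | Investigator-judged yes/no, not derived from CBC values |
| Adverse event tables | Serious events, and related non-serious events | Non-serious cytopenia judged unrelated |

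**3. What the visit summaries would print.** Everything in this step is assumed except the number of patients and the grades.

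- Number of patients: about 37 for study 202, which is half of the 74 in Protocol 1.1. The number with a CBC at a given visit is not stated, so 20 and 50 are also shown.
- Assumed normal values: hemoglobin mean 14, SD 1.3 g/dL; platelets mean 220,000, SD 55,000/mm3; neutrophils mean 3,000, SD 900/mm3.
- Shift in the visit mean from one patient = fall / n.
- The chance that this patient is the visit minimum was simulated (20,000 runs).

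| One patient falls to | Appendix 1 grade | Shift in mean, n = 20 / 37 / 50 | In SDs | Is the visit minimum |
|---|---|---|---|---|
| Hemoglobin 7.5 (fall 6.5) | 2 | 0.33 / 0.18 / 0.13 g/dL | 0.25 / 0.14 / 0.10 | about 100% at each n |
| Platelets 40,000 (fall 180,000) | 3 | 9,000 / 4,865 / 3,600 | 0.16 / 0.09 / 0.07 | 99 / 98 / 97% |
| Neutrophils 600 (fall 2,400) | 3 | 120 / 65 / 48 | 0.13 / 0.07 / 0.05 | 93 / 87 / 83% |

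Milder falls with 37 patients, all outside the Appendix 1 grades, are the visit minimum in 96% of runs (hemoglobin 10), 44% (platelets 110,000) and 11% (neutrophils 1,600). A hemoglobin change of -4 g/dL is the minimum change in 96% to 100% of runs when the SD of change is 0.7 to 1.3.

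So the mean hides one patient and the minimum usually does not. The minimum still cannot give a count. If three of 37 patients had neutrophils of 600 instead of one, the printed minimum would still be 600 and the mean would fall by a further 2 × 2,400 / 37 = 130/mm3, or 130 / 900 = 0.14 SD. Nor can it show persistence, because low minima at two successive visits may come from one patient or from two.

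**The case against.** The strongest case against the point is that the information is already there. Table 14.5.X prints the minimum change as well as the minimum value. Listing 16.2.11 is sorted by study and patient, so each patient's serial values sit together. Protocol 7.2 has an investigator interpret the laboratory reports, and Table 14.4.1 counts hematologic disorders, including important laboratory abnormalities. Malignancy other than basal or squamous cell carcinoma is reportable whatever its cause. Detection happens at the visits, and a table in a final analysis expected in 2018 protects nobody. Protocol 9.2 asks only for a listing and a tabular summary, and both are planned.

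Most of this stands, and it rules out several stronger readings:

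- A reader might infer that CBC is analysed by averages only. It is not, since the extremes of both value and change are planned.
- A reader might infer that one patient's decline would go unseen. The listing, the investigator's review and Table 14.4.1 contradict that.
- A reader might infer that CBC is the only laboratory screen run on every sampled patient. Marking PCR is scheduled at every visit too.
- A reader might compare the shift in the mean with its standard error (for platelets and 37 patients, 4,865 against 55,000 / √37 = 9,042) and call the case lost. No CBC test or interval is planned, and that same patient is the printed minimum in 98% of runs.

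The objection does not supply a count of patients by grade, a shift from baseline, or any sign of persistence derived from the CBC values.

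**Conclusion.** The point holds as a low-cost improvement. The plan meets Protocol 9.2, and a marked fall in one patient would usually be visible somewhere. No planned table can say how many product recipients moved to a worse hematologic grade or stayed there, and unscheduled values, which may be taken because of an adverse event, are outside every CBC summary. An unremarkable Table 14.5.X is therefore weak support for a statement that there was no hematologic signal.

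The absence of a graded or shift table is read directly from the SAP text and shells. The figures for the mean and the minimum rest on assumed normal distributions, means, SDs and visit numbers, and only illustrate the contrast.

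**What to change.** Keep Table 14.5.X. Add one table in the PP population, by study (101, 102, 202) and overall: the number and percentage of patients by worst post-baseline grade against baseline grade, for hemoglobin, neutrophils and platelets, using the Appendix 1 limits. Include unscheduled and repeat values, and show patient IDs for grade 3 or higher. In Listing 16.2.11, flag patients affected at two consecutive visits, and define before database lock what counts as affected. The grade 3 cut-off and the two-visit rule are reporting choices.

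The cost is one extra table and one listing flag, with no new data collection. Programming must confirm that the CRF units match those in Appendix 1 and that neutrophils are available as absolute counts.

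The limitation is that Appendix 1 will not grade milder falls (hemoglobin above 9.4 g/dL, platelets above 99,000/mm3) or rising counts. The existing minimum and maximum remain the summary for these, and the figures above show that the minimum value alone covers milder platelet and neutrophil falls only in part.

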### **8.5. CLINICAL HISTORY**

Individual patient responses (Yes/No/Not Assessed) to the following questions will be recorded at 2.5 years post infusion and all subsequent follow-up visits:

Has the patient,

experienced new or exacerbated haematological disorders (including clinically significant laboratory abnormalities)?

<Protocol: Janssen OZ1-HV1-101/102/202>

<INC code: 1003733>

<SAP Version: 3.0>

---

had any new malignancies (including skin cancers)?

been exposed to possible therapeutic or environmental mutagenic agents?

experienced new or exacerbated pre-existing immunological/rheumatologic disorders?

experienced new or exacerbated pre-existing neurological disorders?

undergone a biopsy or surgical removal of a tumour?

For the last question, patient response to 'Was a sample collected for study assessment?' (Yes/No) will be recorded. If the response is 'Yes', the date of collection, will also be recorded. For the preceding questions, patient response to 'Is this possibly related to the gene transfer product will also be recorded?'

The number and percentage of patients responding 'yes' to the above questions will be tabulated and presented by whether the information was received at a clinical visit, by telephone contact, and overall. The number of patients with clinical history information will also be presented. Percentages within each follow-up visit will be calculated using the number of patients with clinical history information at that visit.

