This will be a follow-up study of patients previously enrolled in the OTH/OZ1-INT-1 trial. All patients in this protocol will be reviewed at six monthly intervals until year 5 post infusion. Thereafter all patients will be reviewed annually, on the anniversary of the infusion until withdrawal or study completion. Patients who were enrolled in the placebo arm will be discontinued after OTH/OZ1-INT-1 has been unblinded.

STUDY POPULATION

Participants in the OTH/OZ1-INT-1 Phase II study entitled “A Randomized Phase II, double blind, controlled trial to evaluate the safety and efficacy of autologous CD34+ hematopoietic progenitor cells transduced with placebo or an anti-HIV-1 ribozyme (OZ1) in patients with HIV-1 infection” will be asked to consent to continue safety monitoring and gene marking as described in this protocol.

DOSAGE AND ADMINISTRATION

All participants of the OTH/OZ1-INT-1 Phase II study received a single dose of placebo or OZ1 transduced CD34+ cells.

SAFETY EVALUATIONS†

Follow-up will be conducted as per current FDA/Center for Biologics Evaluation and Research (CBER) recommendations. Evaluations will include monitoring for related adverse events such as the development of replication competent retrovirus (RCR), predominant integration sites and insertional oncogenesis. Blood samples will be collected for archival storage for assessment of replication competent retrovirus (RCR) and other safety testing as necessary.

EFFICACY EVALUATIONS

Ongoing analysis of quantitative marking of the gene transfer product (OZ1 and LNL6) in peripheral blood mononuclear cells (PBMC) will be performed as part of the testing of predominant integration sites. These marking data will also be analyzed independently of the integration analysis to detect changes in the number of cells carrying the gene transfer product.

TIME AND EVENTS SCHEDULE

Follow up visits may be part of routine clinic visits where possible, but must be performed as described in the Time and Events Schedule. Additional unscheduled visits will be made if clinical or biological findings, as described in this protocol, require additional evaluation or investigation or as directed by the Investigator.

OZ1: Clinical Protocol OZ1-HV1-202 Amendment 4; 07 June 2017

TIME AND EVENTS SCHEDULE[†]

Follow up visit	Yr 2.5	Yr 3	Yr 3.5	Yr 4	Yr 4.5	Annual Yr 5+ /End-of- Study ⁴
Clinical history and examination	X	X	X	X	X	X
Complete Blood Count/Differential and Platelets	X	X	X	X	X	X
Plasma archive		X		X		X

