9. STATISTICAL METHODS[†]

Statistical analysis of data collected during the long term follow-up study will be performed every 5 years. After patients complete an End-of Study visit, the final analysis of data will be done. The primary focus of analysis will be descriptive summarizing changes over time. Patterns over time will be analysed using appropriate techniques. Factors associated with quantitative changes may be assessed.

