Appendix 2:[†]
TELEPHONE FOLLOW-UP QUESTIONNAIRE
FOR SEMI-ANNUAL, ANNUAL, OR END-OF-STUDY REVIEW OF CLINICAL HISTORY

Instructions for Interviewer: This interview will be conducted over the phone by a study investigator only if a patient is unable to be reviewed in the clinic.

SUBJECT NAME:

Date of Birth: |__|_| - |__|_|_|_| - |__|_|
 DD MMM YY

INTERVIEWER SIGNATURE:

Date of Interview: |__|_| - |__|_|_|_| - |__|_|
 DD MMM YY

Study Physician: Circle all appropriate answers for PARTS A, B & C. If respondent answers 'yes' to any of the PART A questions, complete sub-sections and add any additional comments.

All questions refer to the time since the since the last study visit or interview.

PART A: Targeted Review of Clinical History

Please elicit a history to determine whether the subject currently has or has experienced any of the following diseases/conditions (new or exacerbation of existing) since the last review.

Disease, condition or problem	Approximately when did they FIRST notice this condition?	Over the past 12 months have they seen a health care provider for this condition?	Over the past 12 months, have they been hospitalized for this condition?	Study Physician's Comments including Diagnosis

1. New or exacerbated hematologic disorders including laboratory abnormalities?
 
 No (skip to Q2)
 
 Yes
	

 
 dd mm yy 
	
No.....
 
Yes...
	
No
 
Yes: (record hospital name)
	
.....
 
.....
 
.....

2. New malignancies including skin cancer?
 
 No (skip to Q3)
 
 Yes
	

 
 dd mm yy 
	
No.....
 
Yes...
	
No
 
Yes: (record hospital name)
	
.....
 
.....
 
.....

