### **3. STUDY DESIGN**

#### **3.1. OVERVIEW OF STUDY DESIGN**

The OZ1-HV1-101, OZ1-HV1-102 and OZ1-HV1-202 studies form the long term follow-up for OZ1. OZ1 comprises a Moloney Murine Leukemia Virus based retroviral vector (LNL6) containing a gene that encodes an anti-human immunodeficiency virus (HIV) ribozyme. It is a recommendation of the United States Food and Drug Administration (FDA) that all individuals receiving retroviral gene transfer products are followed for life.

Patients who participated in the Phase I study “A Marker Study of Therapeutically Transduced CD4+ Peripheral Blood Lymphocytes in HIV discordant twins” were asked to continue long term monitoring under the OZ1-HV1-101 protocol. Patients who participated in the Phase I study “A Phase I Trial of Autologous CD34+ Hematopoietic Progenitor Cells Transduced with an Anti-HIV Ribozyme” were to continued long term monitoring under the OZ1-HV1-102 protocol. Patients who participated in the Phase II study “A randomized Phase II, double blind, controlled trial to evaluate the safety and efficacy of autologous CD34+ hematopoietic progenitor cells transduced with placebo or an anti-HIV ribozyme (OZ1) in patients with HIV-1 infection” continue long term monitoring under the OZ1-HV1-202 protocol. Following completion and unblinding of the Phase II study, patients who were identified as having been enrolled in the placebo arm were subsequently discontinued from the long term follow-up study 202.

All patients in each protocol will be reviewed at 6 month intervals (+/- 6 weeks) until year 5 post infusion. Thereafter, all patients will be reviewed annually (+/- 12 weeks) on the anniversary of their infusion. Given the recommendation to follow patients for life, patients who withdraw from the study or have been lost to follow-up but return for assessments at a later time may be re-instated in their study. Additional unscheduled visits may be made if any clinical or biological findings require further investigation. A schedule detailing the timing of the follow-up visits and the procedures carried out at each visit is presented in Table 1.

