System Organ Class Preferred Term	OZ1-HV1-101 (N=xx)	OZ1-HV1-102 (N=xx)	OZ1-HV1-202 (N=xx)	Overall (N=xx)
SYSTEM ORGAN CLASS 1	2	1	2	5
PREFERRED TERM 1	1	1	1	3
	R0001	R0002	R0003	
PREFERRED TERM 2	1	0	1	2
	R0004		R0005	
SYSTEM ORGAN CLASS 2	1	0	0	1
PREFERRED TERM 1	1	0	0	1
	R0004			
PREFERRED TERM 2	etc..			
ETC				

Note: Data summarized in this table are presented in data listing X.X.X.X  
Death is defined as an AE outcome recorded as fatal and/or a AE seriousness recorded as death

DDMMYYYY HH:MM

Suggest add footnote to define how these are selected (AEs with outcome='fatal')?

<Protocol: Janssen OZ1-HV1-101/102/202>

<INC code: 1003733>

<SAP Version: 3.0>

Janssen - OZ1-HVI-101/102/202

TABLE 14.4.1

Page 1 of x

Clinical History  
 Experienced new or exacerbated pre-existing haematological disorders  
 (including clinically significant laboratory abnormalities)?  
 Summary Statistics: PP Population

Long Term Follow-up Visit	Response	Clinical Visit (N = XX) n (%)	Telephone Contact (N = XX) n (%)	Overall (N = XX) n (%)
2.5 yrs post infusion	N*			
	Yes			
	Related			
	Not Related			
3 yrs post infusion	No			
	Not Assessed			
	N*			
	Yes			
3.5 yrs post infusion	Related			
	Not Related			
	No			
	Not Assessed			
Etc..	Etc..			

Note: Data summarized in this table are presented in data listing X.X.X.X

N\* represents the number of patients responding at each visit and is used as the denominator to calculate percentage

DDMMYYYY HH:MM

Similar tables will appear for:

Had any new malignancies (including skin cancers)?

Been exposed to possible therapeutic or environmental mutagenic agents?

Experienced new or exacerbated pre-existing immunologic/rheumatologic disorders?

<Protocol: Janssen OZ1-HV1-101/102/202>

<INC code: 1003733>

<SAP Version: 3.0>

---

Experienced new or exacerbated pre-existing neurological disorders?  
Undergone a biopsy or surgical removal of a tumor?

<Protocol: Janssen OZ1-HV1-101/102/202>

<INC code: 1003733>

<SAP Version: 3.0>

Janssen - OZ1-HVI-101/102/202

TABLE 14.5.X

Page x of y

CBC/Differential and Platelets  
*Parameter (units)*  
 Summary Statistics: PP Population

		Overall												
Post infusion Visit	----- Result -----							----- Change from Baseline -----						
		mean	std	median	min	max	n	mean	std	median	min	max	n	
2 years														
2.5 years														
3 years														
3.5 years														
4 years														
4.5 years														
5 years														
Etc...														

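### Tables 14.4.1–14.4.6 set 'yes' percentages from 6-month and 12-month look-backs side by side, so at constant risk uncommon new events such as malignancies would step up about two-fold from year 6

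*SAP*

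**What the plan says.** SAP 8.5 lists six clinical-history questions: haematological disorders, malignancies, mutagenic exposure, immunological or rheumatologic disorders, neurological disorders, and biopsy or tumour removal. They are answered at 2.5 years post infusion and at every later visit. On the summary it says: "The number and percentage of patients responding 'yes' to the above questions will be tabulated". On the denominator it says: "Percentages within each follow-up visit will be calculated using the number of patients with clinical history information at that visit". The shell for Table 14.4.1, which is the pattern for the other five tables, agrees: its N* "represents the number of patients responding at each visit and is used as the denominator to calculate percentage". The shell has one block of rows per nominal visit and no column for the interval covered.

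SAP 3.1 sets the spacing: "All patients in each protocol will be reviewed at 6 month intervals (+/- 6 weeks) until year 5 post infusion". It continues: "Thereafter, all patients will be reviewed annually (+/- 12 weeks) on the anniversary of their infusion". The Overview of Study Design in the Protocol Synopsis gives the same pattern. Protocol 4 and 7.1 exempt the End-of-Study visit from the 12-week window, and Protocol 7.1 and 8 let lost or withdrawn patients re-enter.

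The reference period is explicit only in Protocol Appendix 2, the telephone questionnaire: "All questions refer to the time since the since the last study visit or interview". SAP 8.5 states none.

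Protocol 9 gives the purpose of the analysis: "The primary focus of analysis will be descriptive summarizing changes over time".

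**The concern.** A question about new or exacerbated conditions, asked at each visit, naturally covers the time since the previous contact. A row that covers 12 months collects more events than a row that covers 6 months at the same underlying risk. The tables place these rows one under another as a time course, so the change of visit schedule enters the display as an apparent rise in risk from year 6.

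Late-onset malignancy is a central question of this study, because insertional oncogenesis is an objective (Protocol 2, SAP 2). The only time-adjusted analysis, SAP 8.2.4, covers related SAEs, so malignancies judged unrelated get no rate. Non-serious events enter the adverse-event data only if considered related (Protocol 10.2, SAP 8.2). For non-serious, unrelated disorders the 14.4 tables are therefore the only planned summary of events over time.

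**Working it through.** The documents state no event rate, power or sample size on this point, so there is no plan figure to reproduce. The rates below are assumptions, shown over a range.

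**Inputs.** The look-back is t = 0.5 years for the rows at years 2.5 to 5 and t = 1 year from year 6 (SAP 3.1). The year 5 visit still looks back 6 months, so the step first shows at year 6. For clinic visits, the assumption is that the reference period runs from the previous contact.

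**Model.** With a constant hazard h = −ln(1 − annual risk), the expected 'yes' proportion is P(t) = 1 − exp(−h·t). The ratio of a 12-month row to a 6-month row is 1 + exp(−h/2).

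| Assumed annual risk | 6-month row | 12-month row | Ratio |
|---|---|---|---|
| 2% | 1.01% | 2.00% | 1.99 |
| 5% | 2.53% | 5.00% | 1.97 |
| 10% | 5.13% | 10.00% | 1.95 |

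**Where the two-fold figure weakens.**

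- Frequent events: the ratio is 1.90 at h = 0.20 per year (9.52% against 18.13%), 1.78 at h = 0.5 and 1.61 at h = 1.0.
- Conditions reported again at every visit: with h = 0.02 and 2% of patients always answering 'yes', the rows are 2.98% and 3.94%, a ratio of 1.32. With 5% always answering 'yes' they are 5.95% and 6.88%, a ratio of 1.16.
- Visit windows: if ±6 and ±12 weeks apply to the intervals, the ratio of look-backs can run from 1.25 to 3.19 around the nominal 2.

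**Longer gaps.** At 5% annual risk a patient with a 24-month look-back has a 9.75% chance of a 'yes' (1 − 0.95²). If 10% of a 12-month row had such a gap, the row would show 0.9 × 5.0% + 0.1 × 9.75% ≈ 5.5% instead of 5.0%. The 10% is an assumption, since the documents give no frequency of gaps.

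**Counts.** Protocol 1.1 gives 74 patients to be enrolled in the placebo-controlled protocol, about half on OZ1, so about 37. At h = 0.02 the expected number of 'yes' answers is 37 × 0.00995 = 0.37 at a 6-month visit and 37 × 0.0198 = 0.73 at a 12-month visit.

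**Check of the remedy.** Dividing by the years covered, the 5% case gives 2.53/0.5 = 5.06 and 5.00/1 = 5.00 per 100 patient-years. The 2% case gives 2.01 and 2.00, and the 10% case 10.26 and 10.00. The step is gone. For the chronic example the per-visit rate over-corrects: 2.98/0.5 ≈ 6.0 against 3.94/1 ≈ 3.9. Twelve-month bands with each patient counted once per band avoid this, because the two 6-monthly visits then count as one annual look-back.

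**The case against.** Several points limit the concern.

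- The phrase about the last visit or interview belongs to a form used only when a patient cannot be reviewed in clinic. The clinic case report form is not among the documents, and the questions on mutagenic exposure and on biopsy or tumour removal do not ask about new or exacerbated conditions. This stands: for clinic visits the look-back is an inference, though a reasonable one, and the missing reference period is itself a gap in SAP 8.5.
- The tables are descriptive, with no test or decision rule, and their rows are labelled by years post infusion, so a careful reader can see the spacing. With fewer than one expected malignancy per row in study 202 at a 2% rate, the step may not show in any single row. This also stands, but the distortion is systematic across all annual against all 6-monthly rows.
- Malignancies also appear as SAEs in Tables 14.3.1 to 14.3.3 and in Listings 16.2.8.2 and 16.2.12. This is partial mitigation, because none of these gives a rate for events judged unrelated.

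A reader might infer that every clinical-history item doubles after year 5, or that returning patients push whole rows to several times their value. The documents support neither. Four of the six tables concern chronic disorders or exposures that can be reported repeatedly. Multi-year look-backs belong to individual patients, and telephone interviews and secondary contacts exist to limit such gaps (Protocol 7.1).

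**Conclusion.** The weakness is real and of moderate size. It is clearest for new malignancies (Table 14.4.2), where constant risk would give rows from year 6 about 1.9 to 2.0 times the 6-monthly rows. This rests on nominal visit spacing, an event rate of up to about 0.20 per patient-year, events that are not re-reported, and a look-back to the previous contact at clinic visits as well as by telephone. For frequent, recurrent or chronic conditions the step is smaller, and occasional long gaps add little. The End-of-Study row can be distorted in either direction, since its interval is not fixed.

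It would go too far to conclude that a genuine late rise in malignancy could not be detected at all, because the SAE tables and patient-level listings remain. The documents do support a narrower conclusion: as laid out, these tables do not separate a late rise from the change in visit spacing. The correction is cheap and worth making.

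**What to change.** 1. State in SAP 8.5 that each answer refers to the time since the patient's previous contact, whether by clinic visit or telephone.
2. In Tables 14.4.1 to 14.4.6 add the patient-years since each patient's previous contact and the number of patients with a 'yes' per 100 patient-years. Preferably use 12-month bands since infusion (2–3, 3–4, 4–5, 5–6 years and so on), with each patient counted once per band. Keep the raw counts.
3. Footnote the change from 6-monthly to annual visits after year 5 and the unfixed interval of the End-of-Study visit.
4. Assign events by contact interval. Do not use the date on which the condition was first noticed: it is shown only on the telephone form, and for an exacerbated disorder it can predate follow-up.

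The cost is a change to SAP wording and shells and a little extra programming. Infusion and visit dates are already needed for SAP 6.4, and patient-years are already derived for SAP 8.2.4. The downside is that rates will be imprecise at these counts, which is why the raw counts should stay beside them.
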